TITLE: Colorectal Cancer Screening in Alaska Native Men

NCT: 06436300

VERSION: June 30, 2023

TABLE OF CONTENTS

A. Objective.....	2
B. Background.....	2
C. Study Protocol.....	2
D. Statistical Analysis.....	4
E. Plan for Dissemination.....	5
F. References.....	5

A. Objective

Conduct a randomized controlled trial to test the effect of the adapted motivational messaging intervention on colorectal cancer (CRC) screening with Alaska Native and American Indian (ANAI) men.

B. Background

ANAI men in Alaska experience the most profound CRC disparities of any US racial or ethnic group. In 2019 the American Cancer Society reported a CRC incidence of 100 per 100,000 for ANAI men, nearly twice the next highest incidence (58 per 100,000) for non-Hispanic Blacks, and more than twice that for non-Hispanic Whites (46 per 100,000).¹ Similarly, CRC mortality in ANAI men was nearly twice the rate for non-Hispanic Blacks (47 vs. 26 per 100,000) and almost triple that for non-Hispanic Whites (17 per 100,000).

Approximately half of CRC deaths could be prevented by screening, which detects lesions in pre-cancerous or early-stage disease, when 5-year survival rates are much higher.^{2,3} Current guidelines recommend CRC screening for average-risk adults starting at 45-50 years old, but those in high-risk groups (such as ANs) should start at younger ages.^{4,5}

Nationwide, 58%-65% of non-Hispanic Whites meet CRC screening guidelines, compared to 45%-54% of ANAI people.^{6,7}

In 2013 our team designed a text

messaging intervention to promote CRC screening among ANAI customer-owners at Southcentral Foundation (SCF). The intervention involved sending up to 3 culturally informed text messages at 1-month intervals. All messages exclusively promoted colonoscopy. In a randomized controlled trial (RCT) with 2,386 customer-owners 40-75 years old, our intervention led to a 50% increase in CRC screening in ANAI women – but it had no effect in ANAI men.⁸

In light of these findings, the current study will test a version of the text messaging intervention that has been further adapted for ANAI men.

C. Study Protocol

C.1. Study Design and Outcomes

This is a parallel-arm randomized controlled trial with four study conditions: usual care control; or usual care plus text messaging only (“Messages”), text messaging and promise of a \$50 gift card for completing CRC screening (“Gift Card”), or text messaging and promise of being entered into a raffle (~\$200 prize value) for completing screening (“Raffle”).

The original primary outcome was any completed CRC screening documented in the electronic medical record (EMR) during follow-up. During the intervention adaptation process, in response to community partner feedback we added scheduling a pre-screening visit or screening procedure as an additional primary outcome.

C.2 Randomized Trial. The RCT will be implemented over approximately six months. We will query the EMR to randomly select 1000 male ANAI customer-owners aged 40-75 years who are eligible for routine CRC screening. The cohort will be further randomized into one of the four study arms. Randomization will be

[figure not shown]

Figure 1. Randomized Controlled Trial Study Design. (Note the figure reflects a three-month follow-up; we were able to revise the timeline to allow six months of follow-up.)

matched and stratified by age (40-49, 50-75) and location (Anchorage, Matanuska-Susitna Valley) to ensure balance of these factors in the study arms. **Figure 1** depicts the RCT study design. The age range of participants reflects SCF clinical practice guidelines, as well as the earlier mean age at CRC incidence among ANAI people compared with other races and ethnicities.

Intervention details

The intervention comprises a series of up to four electronic messages delivered by text to a mobile phone and/or by email. Messages are sent approximately 2 weeks apart (total duration = 6 weeks). After sending each message, we will query the EHR so that men who have completed screening do not continue receiving messages. Men who have scheduled but not completed screening will not be removed from the list, due to high rates of no-shows for colonoscopy appointments. For men in the three intervention arms who are still unscreened and therefore eligible to receive the fourth message, we will select a random subset to receive an unsolicited mailed packet containing the Fecal Immunochemical Test (FIT) kit with a pre-paid return envelope to the mailing address on file. The total sample size for this subgroup will depend on costs and logistical feasibility, but we anticipate sending approximately 125 kits per arm (approximate total 375). Anchorage-empaneled CO FIT kits will be returned to the SCF CRC team mailbox in MSD administration. The CRC team will receive the completed FIT kits and send the samples down to the ANPCC lab for processing. Valley-empaneled CO kits will be returned to VNPCC lab, which will be prepared and sent via courier to ANMC lab. The fourth message will be different for men who are and are not randomly selected to receive unsolicited mailed FIT kits. For men who are not selected, the message will encourage them to call and request a mailed kit. For men who are selected, the message will inform men that they will receive a kit for completing a FIT screening at home. To ensure equitable access to receiving incentives, all study participants in any of the four arms who complete CRC screening before the final data query will receive a gift card and will be included in the raffle.

Messages will be personalized by including the recipient's name in the message salutation. SCF phone numbers and videos will be hyperlinked for participant convenience. The messages will include an option to respond with "SCF" if the participant wishes to be contacted by SCF about screening options. If a participant responds "SCF", they will receive an automated response message and their primary care team will be notified of their interest. If a participant responds "Stop", they will not receive an automated response message and no further messages will be sent.

All men who complete colorectal cancer screening will receive the gift card incentive and be entered in the raffle, even if they were not informed in advance that this was possible. After the RCT is completed, we will send a final message to all men who did not receive any messages about gift card or raffle incentives and who did not complete screening during the study period. This message will inform the men that they can receive a gift card and be entered into a raffle if they complete screening within the next four weeks, and it will include the same contact information for accessing screening as the first message in Table 1.

Sample Size, Eligibility, Randomization, Recruitment/Informed Consent, and Compensation

One thousand customer-owners will be randomized in the RCT, with 250 assigned to each of the four study arms (**Figure 1**). Inclusion criteria are 1) male; 2) ANAI; 3) active SCF customer-owners; 3) aged 40-75; 4) no history of CRC or abnormal screening; and 5) due for CRC screening. Individuals who meet inclusion criteria but are at increased/high risk of CRC relative to race-, age-, and gender-matched peers (e.g., due to family history of CRC) are not eligible to participate.

The EMR will be queried to identify customer-owners eligible to participate in the study and to extract data for study outcomes. Only those individuals who are (1) members of the study team who and (2) members of the SCF Data Services department will have access to identifiable customer-owner information or be directly involved in the following study activities: determining the eligibility of customer-owners; de-identifying the data of eligible customer-owners; randomizing eligible customer-owners to control or intervention arms of the RCT; sending motivational messages to eligible customer-owners; and sharing fully de-identified participant data with other members of the study team for analysis.

All study data will be obtained directly from the EMR and will therefore not involve active recruitment of any individual patient. Additionally, study data will not include any identifiable customer-owner information. We

have obtained a waiver of consent, which was granted warranted because 1) our study is designed to increase uptake of existing screening guidelines; 2) the intervention will not interfere with usual care; and 3) directly recruiting and consenting participants into the RCT might lead to heightened awareness and uptake of CRC screening, which could increase the risk of Type 2 error (failure to detect a beneficial intervention effect) in the RCT. All messages sent to customer-owners will include instructions for opting out of further communications.

There is no compensation provided for the RCT, because no customer-owner will be asked to contribute any time or effort to completing an intervention or engaging in data collection.

Data Collection

All study data will be obtained from the EMR. SCF Data Services staff will extract and de-identify data, and assign unique study IDs to individuals included in the dataset. De-identified data will be securely transmitted to [name] at Washington State University for analysis. The dataset will be stored on a HIPPA-compliant secure server that is backed up daily to an off-side location. Files at Washington State University will be password protected and accessible only to [name]. A member of the study team who also works in the SCF Data Services will retain a second copy of the de-identified study dataset on a password-protected, secure network server at SCF. **Table 1** lists the variables that will be extracted from the EMR.

Table 1. Measures to be extracted from the electronic medical record for the RCT

Variable	Categories or Units	Intended use
Age	40-45; 46-49; 50-59; 60-75	Eligibility, cohort description, subgroup analyses
Gender	Men only	Eligibility
Race	ANAI only	Eligibility
Screening history	Only people without previous abnormal CRC screening results	Eligibility
CRC history	Only people with no previous CRC diagnosis	Eligibility
Location	Urban/suburban; rural	Cohort description, subgroup analyses
Previous CRC screening history	Never screened at SCF; previously screened by colonoscopy; previously screened by other method	Cohort description, subgroup analyses
Duration of overdue screening eligibility	Years (to 1 decimal place)	Cohort description, subgroup analyses
Total SCF clinic visits in the past year	Count	Cohort description, subgroup analyses
CRC screening completed	Type of test Month in which test occurs	Primary outcome
CRC screening or pre-screening scheduled	Yes, No	Primary outcome

CRC = colorectal cancer; SCF = Southcentral Foundation

D. Statistical analysis

All data analysis will be conducted with Stata version 16 or later (StataCorp, College Station, TX) or R statistical software packages. We will report descriptive statistics for all study variables as counts and frequencies for categorical factors, and as means, standard deviations, and ranges for continuous factors. Descriptive results will be presented separately for men in the intervention and control conditions. Our inferential analysis will use an intent-to-treat approach, using data for all participants in the group to which they were assigned, regardless of events that occur after randomization. We will use logistic regression with marginal standardization to estimate the effect of the intervention on CRC screening. Results will be presented as risk ratios and risk differences with 95% confidence intervals. Marginal standardization estimates are

interpreted as the difference in CRC screening if everyone received the intervention compared to screening if no one received the intervention, in a population with the same distribution of regression model covariates as observed in the study sample. If deemed appropriate, the regression model specification may be adjusted (e.g., binomial regression) prior to conducting the statistical analysis. Our primary analysis will estimate the effect of assignment to the intervention group without adjusting for any covariates, as appropriate for a large RCT. Sensitivity analyses will adjust for any other variables that appear unbalanced between groups at baseline, and secondary analyses will evaluate potential modification of intervention effectiveness by variables such as age, location, and history of CRC screening.

E. Plan for Dissemination

Results from this study will be submitted for publication in the peer-reviewed literature and/or for presentation at scientific conferences. We will also seek out opportunities to share results with SCF and Tribal leadership, customer-owners, and other stakeholders. Documents containing study results (e.g., manuscripts, presentations) will not be made available to the public unless they have first been reviewed and approved by SCF Tribal Review.

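### Could the post-trial incentive message add bookings to the scheduling primary in the control and Messages arms only?

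*Combined protocol and SAP*

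**What the plan says.** Section C.1 first defines completed screening, counted over follow-up. The next sentence reports that "we added scheduling a pre-screening visit or screening procedure as an additional primary outcome", with no window restated. The note to Figure 1 in C.2 says that "we were able to revise the timeline to allow six months of follow-up".

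Under Data Collection, Table 1 "lists the variables that will be extracted from the EMR". Completed screening carries the test type and "Month in which test occurs". The row "CRC screening or pre-screening scheduled" is only Yes or No.

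Two statements under Intervention details (C.2) concern incentives:

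- During the trial, "all study participants in any of the four arms who complete CRC screening before the final data query will receive a gift card", and is entered in the raffle.
- Once the trial is over, "we will send a final message to all men who did not receive any messages about gift card or raffle incentives" and who were still unscreened at the end of the study period. They are told that "they can receive a gift card and be entered into a raffle if they complete screening within the next four weeks".

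By design the men with no incentive messages are the control and Messages arms. No sentence dates the final data query or places it before or after this message.

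**The concern.** The post-trial offer reaches two of the four arms, so randomization would not balance any bookings it prompts. Suppose the outcome query ran after the four-week offer and the scheduling flag had no cut-off. Those bookings would count as events in control and Messages but not in Gift Card or Raffle. The incentive arms would then look less effective than they are, against control and against Messages, on a primary outcome. Intention-to-treat analysis would not help, because the extra events sit in the assigned arms. Completed tests could be trimmed by month, but an undated Yes/No could not be trimmed by the analyst who receives it. Honouring the offer also requires some look at the records after the four weeks, so a late query is not fanciful.

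**Working it through.** **Order of events.** The documents give no direct statement, so the passages have to be set side by side.

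1. The final message is sent after the trial is complete. Its recipients are defined by not having been screened during the study period. Choosing them requires a closed study period and a check of completion before the message goes out.
2. Men in all four arms who are screened before the final data query already receive the incentive. A separate four-week deadline for the later message makes most sense if that query is already done.
3. Record checks for operational reasons are separate from outcome extraction: the plan queries the record after every message just to stop contacting screened men. A later check to pay incentives would be another of these.
4. Southcentral Foundation Data Services, with access to identifiable records, extracts and de-identifies the data. A Yes/No flag can be limited to a window when it is created. A flag drawn at the close of follow-up, before the message, cannot contain later bookings at all.

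On this reading the bias is zero.

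**Size if the order were reversed.** The plan supplies 250 men per arm (4 × 250 = 1000, its stated total). Every rate below is an assumption.

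- Per man: 2.5/250 = 1.0 point off Gift Card v control or Raffle v control.
- Assume 10% booking in control and 15% in each messaging arm over 26 weeks. Background booking in four further weeks, taken as equal in all arms: b = 0.10 × 4/26 = 1.54 points.
- If the message multiplies four-week booking by m, the excess is g = b(m − 1). Control becomes 0.10 + b + g, and Gift Card 0.15 + b = 16.54%.

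| m | g, points (men of 250) | Control | Gift Card v control RD, points | RR |
|---|---|---|---|---|
| 1 | 0 | 11.54% | 5.0 | 1.43 |
| 1.5 | 0.77 (1.9) | 12.31% | 4.2 | 1.34 |
| 2 | 1.54 (3.8) | 13.08% | 3.5 | 1.26 |
| 3 | 3.08 (7.7) | 14.62% | 1.9 | 1.13 |

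The six-month risk ratio is 0.15/0.10 = 1.50. Four extra weeks of background booking alone bring it to 1.43, so only the fall from 1.43 is due to the message.

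Other contrasts under the same assumptions:

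- Messages v control keeps a 5.0-point difference, because both arms gain g.
- Gift Card v Messages, if truly equal, reads −g: −0.8, −1.5 or −3.1 points.
- The three messaging arms pooled against control read 5.0 − (2/3)g = 4.5, 4.0 or 2.9 points, provided Messages men respond as control men do.

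A second set of assumed rates gives the same direction. Take 25% v 15%, with 5% of unbooked control men responding. Control becomes 0.15 + 0.05 × 0.85 = 19.25%, the risk difference falls from 10.0 to 5.75 points, and power at an assumed two-sided 5% level falls from 80% to 34%.

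**Start of the window.** Men already booked at randomization are not excluded, but randomization balances them. If a share e is already booked, RD = (1 − e) × 5.0 points: 4.9, 4.75 or 4.5 for e = 2%, 5% or 10%. This is mild dilution, not bias between arms.

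**The case for a change.** The strongest reply is that a primary outcome should not depend on inference. The window is written for completed screening and not repeated for scheduling, the final query is undated, and an undated flag gives a reader no means of confirming that a cut-off was applied. The error, if it occurred, would be directional, and under 8 extra control bookings would take a 5.0-point difference to 1.9 in the illustration. A sentence and one date field would remove the doubt cheaply.

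The textual facts in this stand. What does not stand is the step from an unstated order to a likely error. The harm needs the outcome flag to be drawn after a message that the plan places after the trial, and also to be drawn without the follow-up limit attached to the other primary outcome. Nothing in the plan directs either. Nor does the lack of a date in the analyst's file stop Data Services from applying the limit at extraction. That assumes the source record holds booking dates, or that the flag is drawn at the close of follow-up; the documents state neither, but the second is the ordinary course.

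It is also true that the plan does not say whether a kit request or a completed mailed kit counts as scheduling, and that section D does not name scheduling. The first is a definitional choice with arguments both ways, since unsolicited kits go only to the messaging arms. The second is filled by applying the stated model to both primary outcomes.

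**Conclusion.** This is a gap in wording that analysts would fill sensibly, and it does not call for a change. Read as a whole, the plan counts both primary outcomes over six months and sends the extra offer afterwards, so the bias is zero. The conclusion rests on two inferences: that scheduling shares the follow-up stated for completed screening, and that the outcome flag is drawn, or cut off, before the final message. If both failed, Gift Card and Raffle would be understated against control by 1.0 point per 2.5 prompted control bookings, while the Messages v control difference would change little. The documents give no booking rate or response to the message, so the larger figures above show what assumed rates would do and are not estimates for this trial.

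### Unsolicited FIT kits go to about half of each intervention arm and to no control man, so the planned completed-screening contrast with control is a package effect, not the messaging effect in the objective

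*Combined protocol and SAP*

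**What the plan says.** Section A sets the objective as testing the adapted messaging intervention. Section C.1 describes the arms as "usual care control; or usual care plus text messaging only" and two arms that add a promised gift card or raffle entry. No arm description mentions a kit. C.2, Intervention details, opens with "The intervention comprises a series of up to four electronic messages delivered by text to a mobile phone and/or by email".

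The same paragraph then introduces the mailing: "For men in the three intervention arms who are still unscreened and therefore eligible to receive the fourth message, we will select a random subset"; they are sent a FIT kit with a pre-paid return envelope. On numbers, "we anticipate sending approximately 125 kits per arm (approximate total 375"), with the caveat that "The total sample size for this subgroup will depend on costs and logistical feasibility". The fourth message differs by selection. One group is prompted to ask: "For men who are not selected, the message will encourage them to call and request a mailed kit". The other group is told that a kit is on its way: "For men who are selected, the message will inform men that they will receive a kit for completing a FIT screening at home".

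On outcomes, C.1 says "The original primary outcome was any completed CRC screening documented in the electronic medical record (EMR) during follow-up"; scheduling was added later as a further primary outcome. Section D analyzes all men in their assigned group, unadjusted. Its secondary analyses name age, location and screening history. It mentions neither FIT, nor kits, nor the second random selection.

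**The concern.** Control men cannot be selected for a kit through the study, and a returned kit is itself a primary-outcome event. The contrast of any intervention arm with control therefore mixes two effects: that of the messages and that of having a test arrive in the mail. Section D does not say which it means by the intervention. The definition in C.2 and the arm label in C.1 both point to messages. The size of the mixture also depends on how many kits the budget allows.

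The Background reports that the earlier text-message trial had no effect in men, so whether adapted messages work in men is the central question. If the messages do nothing but men return kits, the plan followed exactly could report a significant effect, and readers could adopt messaging alone because of it. The randomized data that separate messages from kits will exist, but the plan does not use them.

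The concern is limited to contrasts with control on completed screening. It makes no claim about the scheduling outcome.

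**Working it through.** **Figures in the plan.** 3 × 125 = 375 kits and 4 × 250 = 1,000 men; both agree with the text. The kit share is 125/250 = 50% of each intervention arm and 0/250 of control. The plan gives no screening rate, kit return rate, significance level or power, so everything below rests on assumed inputs.

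**Assumptions.**
- Zero message effect.
- Control completion *c* of 5%, 10%, 20% or 30%.
- A quarter of screening occurs before kit selection.
- A mailed man who would not otherwise screen returns the kit with probability *r* of 5%, 10% or 20%.
- Two-sided 5% test.

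**Shift from kits alone.**
- early = 0.25*c*
- late = (*c* − early)/(1 − early)
- added risk = kits × (1 − late) × *r* / 250

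At *c* = 10% and *r* = 10%: early = 0.025; late = 0.075/0.975 = 0.0769; added risk = 125 × 0.9231 × 0.10/250 = 0.046, or 4.6 points. At *r* = 5% and 20% it is 2.3 and 9.2 points. The messages-alone effect is 0 throughout.

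**Chance of a significant contrast with control** (two-proportion normal test, pooled variance; 250 v 250 / 750 v 250):

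| Kit return | *c* = 5% | *c* = 10% | *c* = 20% | *c* = 30% |
|---|---|---|---|---|
| 5% | 20% / 24% | 13% / 15% | 9% / 10% | 7% / 8% |
| 10% | 54% / 67% | 35% / 45% | 21% / 27% | 15% / 19% |
| 20% | 95% / 99% or more | 83% / 95% | 59% / 76% | 43% / 58% |

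The chance exceeds 50% in 4 of 12 one-arm cells and 5 of 12 pooled cells. If 10% or 50% of screening comes before kit selection, no cell moves by more than about 7 points.

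**Dependence on the kit budget** (*c* = 10%, *r* = 10%). With 100 kits per arm the shift is 100 × 0.9231 × 0.10/250 = 3.7 points, and the chances are 25% / 32%. With 150 kits it is 5.5 points and 46% / 59%.

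**Contrasts among the three intervention arms.** With equal kits and no true difference, the shift is 0. A true 10-point difference shrinks to about 9.8 points at 5% return, 9.6 at 10% and 9.1 to 9.2 at 20%. These contrasts are largely spared. With 100 v 150 kits, the shift is 1.5 to 3.7 points over *c* = 10% to 30% and *r* = 10% to 20%.

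**Can the message effect be recovered?** Yes, because selection is random among unscreened men. Weight unselected eligible men by eligible/(eligible − selected), give selected men weight 0, and give all others weight 1. With *e* the early risk (a quarter of that arm's risk) and *q* its late risk, the variance of the weighted arm risk is

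*e*(1 − *e*)(1 − *q*)²/250 + (1 − *e*)²*q*(1 − *q*)/(eligible − 125).

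Example, 10% v 15%. In the intervention arm *e* = 0.0375, *q* = 0.1125/0.9625 = 0.117, and eligible = 250 × 0.9625 = 240.6, leaving 115.6 unselected. The arm variance is 0.00094, against 0.15 × 0.85/250 = 0.00051 unweighted. The control variance is 0.10 × 0.90/250 = 0.00036. The contrast SE is √0.00130 = 0.036 against √0.00087 = 0.0295, a ratio of 1.22. Over the four control rates and effects of 0, 5 and 10 points, the ratio is 1.18 to 1.27 for one arm and 1.09 to 1.18 pooled.

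In simulation (20,000 trials per scenario, zero effect), the mean weighted difference was within 0.03 points of zero. It was significant in 5.0% to 5.5% of trials, and the robust SE was 0.99 to 1.00 of the empirical SE.

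**The case against.** The strongest reply is that the kit belongs to the assigned strategy. The kit text sits under Intervention details, applies to all three intervention arms and is announced in the fourth message. Section D estimates the effect of assignment whatever happens later. On that reading the contrast is right, and the word 'only' in C.1 merely separates the Messages arm from the two incentive arms. This much stands: the as-assigned contrast is valid for the package. But Section D does not say that the kit is included, C.2 defines the intervention as messages, and Section A asks about messaging.

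A second reply is that Table 1 extracts test type and month, and Section D promises descriptive statistics by condition, so an excess of late FITs could be seen. That helps, but it does not separate unsolicited kits from requested ones and gives no estimate of the message effect.

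A third is that the size rests wholly on assumed rates and is modest in many cells; at 5% return the one-arm chance is only 7% to 20%. This is fair, and it is why the whole range is shown.

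A fourth is that the kit-free contrast is imprecise and not purely messages, since unselected men are prompted to request a kit. Both are true. The prompt is part of the message and should be stated. The imprecision is the reason to make this contrast key secondary. As a result the messaging question has no confirmatory test of its own, and the report should say so.

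**Conclusion.** The concern holds and should be fixed. The study's unsolicited kits go to about half of each intervention arm and to no control man. Section D has no kit term, so a kit effect on completed screening can be credited to messages. With zero message effect, the chance of a significant contrast ranges from 7% to 95% for one arm and from 8% to at least 99% pooled. It depends on control rates of 5% to 30% and kit returns of 5% to 20%, all assumed. The textual gap is certain; the size of its consequence is not. The documents do not say whether usual care itself mails kits, and if it does the shift could be smaller. Randomization and the as-assigned analysis are sound. What is wrong is the unstated estimand and the unused second randomization.

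**What to change.** In Section D:

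1. Keep the as-assigned contrast with control as primary, label it *messages plus unsolicited mailed FIT to about half*, and do not describe it as the effect of messages alone.
2. Prespecify a kit-free contrast with control as key secondary, with robust standard errors. Weights: 1 for control men and for intervention men not eligible for kit selection; eligible/(eligible − selected) for unselected eligible men; 0 for selected men. Compute weights within arm and within any stratum used for selection. The protocol describes no such strata, but they would matter. With two equal strata at half and 1.5 times the mean risk, 10% control and kits split 30/70 or 70/30, weights that ignore strata are off by −1.7 or +1.6 points; within-stratum weights are off by 0.0. Base statements about messages alone on this contrast, and say that unselected men are still prompted to request a kit.
3. Add selected v unselected among eligible men, stratified by arm, described as *mailed kit plus announcement v prompt to request a kit*. At 10% return its power over three arms is 99%, 97%, 80% and 60% at 5%, 10%, 20% and 30% control.
4. Report items 2 and 3 as estimates with 95% CIs and no confirmatory claim.
5. Carry kit-eligibility and kit-selection flags in the analysis dataset, and state whether men who replied Stop are in the eligible set.

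**Cost.** SAP wording and two flags, with no change to conduct and no extra participants. The statistical price falls on item 2, which gives weight 0 to about 375 of 750 intervention men. Its power against that of the as-assigned contrast (unpooled SE) is:

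| Control v intervention | One arm | Pooled |
|---|---|---|
| 10% v 20% | 72% v 88% | 95% v 99% |
| 10% v 15% (the 50% relative increase reported for women) | 28% v 40% | 49% v 58% |
| 20% v 25% | about 20% v 27% | 32% v 39% |

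Simulated kit-free power for 10% v 15% was 26% for one arm and 48% pooled. A null kit-free result must not be read as showing that messages have no effect.

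### Randomization is stratified by age and location but the primary analysis ignores both, so its intervals are too wide if either factor predicts screening

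*Combined protocol and SAP*

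**What the plan says.** - **Design (Section C.2).** Randomization is "matched and stratified by age (40-49, 50-75) and location (Anchorage, Matanuska-Susitna Valley) to ensure balance of these factors in the study arms". The section on sample size and randomization allocates 1000 men, "with 250 assigned to each of the four study arms".
- **Primary analysis (Section D).** Logistic regression with marginal standardization gives risk ratios and risk differences with 95% confidence intervals. On covariates the plan states: "Our primary analysis will estimate the effect of assignment to the intervention group without adjusting for any covariates, as appropriate for a large RCT".
- **Other analyses (Section D).** Sensitivity analyses adjust only for other variables that look unbalanced at baseline. Age and location are balanced by design, so that trigger would not bring them in. They are otherwise named as possible effect modifiers in secondary analyses. Nothing corrects the primary standard error for the stratified design.
- **Data (Table 1).** Age is held as "40-45; 46-49; 50-59; 60-75", which collapses exactly to the two age strata. Location is held as "Urban/suburban; rural", which is not the stratification factor.

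**The concern.** Stratified allocation removes chance differences between arms in the stratifying factors. If those factors predict screening, arm differences vary less from trial to trial than under simple randomization. A model containing only arm does not know this and reports the larger, simple-randomization variance. The interval is then wider than the design warrants and the test rejects too rarely under the null.

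The plan's reason for not adjusting, that the trial is large, does not answer this. The excess is a ratio fixed by how prognostic the strata are, and it is the same at any sample size.

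Power is at stake. The documents state no control rate, target effect or power. If control screening were 10% and the risk ratio 1.5 (both assumed), one arm against control would have only about 40% power. The protocol itself cites the risk of Type 2 error when it justifies the consent waiver.

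**Working it through.** **Plan's own figure.** The only figure to reproduce is 4 × 250 = 1000, which agrees. There is no power calculation to re-derive.

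**Inputs from the documents.** Two age levels by two location levels give four strata; there are 250 men per arm; 95% intervals imply a two-sided 5% test.

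**Assumed inputs.** Stratum shares w = 0.3, 0.2, 0.3, 0.2; control risks p_s by stratum (four scenarios); risk ratio 1.5 in every stratum (the size reported for women in the earlier trial); strata exactly balanced across arms. Both one arm v control (250 v 250) and the three message arms pooled v control (750 v 250) are shown.

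**Formulas.** With P = Σ w·p_s:

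- variance per man reported by the unadjusted model: P(1 − P)
- true variance per man under forced balance: Σ w·p_s(1 − p_s) = P(1 − P) − Σ w(p_s − P)²
- R² = Σ w(p_s − P)² / [P(1 − P)]
- SE ratio at no effect = 1/sqrt(1 − R²)
- actual type I error of the unadjusted test = 2[1 − Φ(1.96 × SE ratio)]
- unadjusted power = Φ[(d − 1.96·SE_u)/SE_t]; adjusted power = Φ[d/SE_t − 1.96]

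Here d is the risk difference, SE_u the unadjusted standard error and SE_t the true one.

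**One scenario in full (3/6/15/25%, 250 v 250).** P = 0.009 + 0.012 + 0.045 + 0.050 = 0.116, so P(1 − P) = 0.102544. The between-stratum part is 0.006784, so R² = 0.0662 and the SE ratio is 1/sqrt(0.9338) = 1.035. At risk ratio 1.5, d = 0.058, SE_u = 0.03139 and SE_t = 0.02995. Unadjusted power = Φ[(0.058 − 0.06152)/0.02995] = 45.3%. Adjusted power = Φ[1.937 − 1.96] = 49.1%.

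**All four scenarios**

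| Assumed stratum risks | R² | SE excess at no effect | Unadjusted type I error | Power 250 v 250, unadjusted v adjusted | Power 750 v 250, unadjusted v adjusted |
|---|---|---|---|---|---|
| 10% throughout | 0 | 0 | 5.0% | 39.6% v 39.6% | 58.4% v 58.4% |
| 6/8/12/15% | 1.3% | 0.7% | 4.85% | 39.5% v 40.1% | 58.5% v 59.1% |
| 3/6/15/25% | 6.6% | 3.5% | 4.25% | 45.3% v 49.1% | 66.3% v 69.3% |
| 5/10/20/35% | 8.7% | 4.7% | 4.0% | 63.8% v 68.6% | 84.4% v 87.0% |

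**Rule of thumb.** R² of 1%, 5% and 10% widens the interval by 0.5%, 2.6% and 5.4%. For one binary factor splitting the sample equally, at 10% overall screening, odds ratios of 2, 3 and 5 widen it by 0.5%, 1.2% and 2.3%.

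**Simulation of the proposed model** (logistic on arm, age and location, standardized, delta-method SE; 100,000 trials per scenario, 250 v 250, unadjusted v adjusted, scenarios in table order):

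- type I error: 5.2% v 5.2%, 4.9% v 5.0%, 4.5% v 5.3%, 4.1% v 5.3%
- power on the risk difference: 39.9% v 40.0%, 39.6% v 40.3%, 45.4% v 49.5%, 64.1% v 68.7%
- power on the log risk ratio, three prognostic scenarios: 38.0% v 38.9%, 44.4% v 48.1%, 63.0% v 67.8%

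The standardized risk difference equalled the crude one in every trial, as it must when strata are exactly balanced.

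**Is stratification the cause?** A separate simulation (200,000 runs; assumed shares 28/12/42/18%, risks from 5% to 40%) gave the unadjusted test a type I error of 4.0% under stratified randomization and 5.1% under simple randomization with the same risks. The conservatism therefore comes from ignoring the stratification.

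**The case against.** The strongest reply is that this is not an invalid analysis. The unadjusted intent-to-treat comparison is stated in advance, is unbiased and errs on the safe side. The gain from adjusting is unknown and may be tiny: nothing in the documents says that age or location predicts screening among average-risk men who are all due for it, and a loss of 4 to 5 points needs a seven- to eightfold spread in risk. The assumed effect comes from women, whereas the earlier trial found none in men. All of this stands. It limits the size of the point, not its direction.

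Part of the simulated gain also comes from the adjusted test running slightly above 5%. In a further simulation (400,000 runs) with the adjusted test held at exactly 5%, the gain was about 0.1 point for 6/8/12/15%, and 3.6 and 4.1 points in the two strong scenarios, against 4.5 and 4.9 without that correction. So the weak-scenario gain all but vanishes, while a real gain remains where the strata matter.

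The identity of crude and adjusted estimates needs exact balance. The allocation mechanism is not described, so small departures would move the estimate slightly. This stands as a condition.

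Finally, Section D names age and location as effect modifiers and lets the model specification change before analysis. Neither provision commits the primary model to the strata.

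**Conclusion.** The point holds, conditionally. If randomization balances age and location as Section C.2 intends, and either predicts screening, the primary standard errors and intervals are too wide and the tests conservative. There is no bias and no inflation of type I error.

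Under the assumed scenarios the power loss is 0 to about 5 points for one arm against control and 0 to about 3 points if the message arms are pooled. Weak strata cost under 1 point; the upper end is an extreme assumption. If neither factor is prognostic, nothing is lost. The direction is certain given those conditions; the size cannot be fixed from the documents. It is an efficiency improvement worth making before analysis.

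**What to change.** - Make the primary model logistic regression on arm plus the two stratification factors (age 40-49 or 50-75; Anchorage or Matanuska-Susitna Valley), followed by the marginal standardization already named. The marginal risk ratio and risk difference remain the estimands. Report the unadjusted estimate as a sensitivity analysis.
- Carry the actual randomization stratum into the de-identified dataset and reconcile Table 1's location categories with Section C.2. The information exists: the staff with identifiable data are responsible for "randomizing eligible customer-owners to control or intervention arms of the RCT", and the kit-return instructions already separate the two locations ("Anchorage-empaneled CO FIT kits will be returned to the SCF CRC team mailbox"; "Valley-empaneled CO kits will be returned to VNPCC lab").
- Optionally, replace adjustment triggered by observed imbalance with covariates named in advance, such as previous screening history and past-year clinic visits, with the form of the visit count fixed. Their gain cannot be computed from the documents.

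The cost is a few sentences in Section D and one extra field. With non-prognostic strata the simulated adjusted model lost nothing (type I error 5.2% either way). With prognostic strata its type I error was 5.0% to 5.3%, a small finite-sample excess.
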